# 8.2.7.1. MRI Sequence Details for the Study

The standard sequences will be used to determine participant eligibility, care and safety.

The exploratory sequences will be used for exploratory analyses only and will not be used for participant management.

This table provides MRI sequences and their timing throughout the study.

Sequences	Study Visits						
	Screening/Before	Visit 4	Visit 8	Visit 12	Visit 19	ED	UV
	first infusion a	Week 4	Week	Week	Week		
			12	24	52		
Standard							
2D FLAIR	X	X	X	X	X	X	X
2D T2	X	X	X	X	X	X	X
GRE	X	X	X	X	X	X	X
DWI	X	X	X	X	X	X	X
3D T1	X	X	X	X	X	X	X
Exploratory							
3D FLAIR	X	X	X	X	X	X	X
3D T2	X	X	X	X	X	X	X
$DTI^b$	X	X	X	X	X	X	X
SWI b	X	X	X	X	X	X	X
Task-Fmri b	X						

Abbreviations: DTI = diffusion tensor imaging; DWI = diffusion-weighted imaging; ED = early discontinuation visit; FLAIR = fluid-attenuated inversion recovery; Fmri = functional magnetic resonance imaging; GRE = gradient echo; SWI = susceptibility weighted imaging; UV = unscheduled visit.

Note: standard sequences denoted by bold text and shaded cells.

<sup>a Performed either with screening MRI or another time prior to first infusion at Visit 2.

<sup>b Perform when or where available.

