4.5. Tertiary/Exploratory Endpoints Analysis

4.5.1. Exploratory MRI sequences

The table below lists exploratory MRI sequences, and pre-specified endpoints for exploratory analyses, as well as scheduled visits for exploratory endpoints. Unscheduled MRIs will be

included for analyses of exploratory endpoints. Information about four dosing regimens will be combined before performing any analysis here.

Table 4.2. Prespecified endpoints for exploratory MRI sequences.

MRI Sequences	Scheduled Visit	Endpoints
3D FLAIR	2, 4, 8, 12, 19	 ARIA-E presence ARIA-E severity White matter disease burden
3D T2	2, 4, 8, 12, 19	PVS (perivascular spaces) score in centrum semi ovale
SWI	2, 4, 8, 12, 19	 Number of new and total ARIA-H microhemorrhages Number of total ARIA-H superficial siderosis
DTI	2, 4, 8, 12, 19	 Whole cortex MD (mean diffusivity), and FW (free water fraction) Hippocampal MD and FW Whole white matter FA (fractional anisotropy)
fMRI	2	Peak activation in occipital cortex (top 200 voxels based on z-scored activation maps)
vMRI	2, 4, 8, 12, 19	 Hippocampal volume, cortical volume, ventricle volume, whole brain volume (all normalized for intracranial volume) Cortical thickness
FLAIR 3D, 3DT2, SWI	2	Vascular risk score for CAA based on Boston 2.0 Criteria

Abbreviations: ARIA = amyloid-related imaging abnormalities; CAA = cerebral amyloid angiopathy; DTI = diffusion tensor imaging; FLAIR = fluid attenuated inversion recovery; FW = free water fraction; fMRI = functional magnet resonance imaging; MD = mean diffusivity; PVS = perivascular spaces; SWI = susceptibility weighted imaging; vMRI = volumetric magnet resonance imaging.

Prediction of ARIA

Logistic regression analyses will be used to assess four types of baseline models to predict ARIA-E incidence at Week 24:

1) The model will include baseline risk factors of ARIA-E: APOE e4 genotype, number of microhemorrhages at baseline (determined by standard safety sequences), presence of superficial siderosis at baseline (determined by standard safety sequences), amyloid centiloid at baseline, mean arterial pressure, and anti-hypertensives.

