- 2) The model will include all baseline exploratory MRI endpoints discussed before. The following markers will also be considered for inclusion to the model: white matter disease burden from 3D FLAIR, number of microhemorrhages at baseline form SWI, cortical superficial siderosis from SWI, PVS in centrum semi ovale, whole cortex MD, whole cortex FW, hippocampal MD and FW, whole white matter FA, fMRI peak activation in occipital cortex, hippocampal volume, cortical volume, ventricle volume, whole brain volume, cortical thickness, and CAA.
- 3) Exploratory MRI endpoints listed above will be added individually to the baseline ARIA-E risk model described in 1.
- 4) The model will include all baseline risk factors described in 1) and all exploratory endpoints described in 2).

AIC (Akaike information criteria) as well as BIC (Bayesian information criteria) statistics will be generated for each proposed model above. While both the AIC and BIC will be generated, the BIC will be used to evaluate the model. In the case of SWI endpoints, the counts of microhemorrhages and superficial siderosis will come from baseline SWI instead of its standard safety MRI equivalent. In the case of 3D FLAIR, white matter burden score will come from 3D FLAIR instead of the standard safety sequence MRI equivalent. An ROC curve (receiver operating characteristic curve) can be plotted from individual ARIA-E risk prediction model and AUC (area under the curve) will be computed to tell how each model is capable of distinguishing between ARIA-E subjects and ARIA-E free subjects. A possible AUC value is between 0.5 and 1, and the larger the AUC, the better the discriminatory ability.

Comparison between standard and exploratory MRI sequences

To assess the agreement of exploratory versus standard MRI sequences at baseline, a contingency table assessing agreement on white matter disease burden, number of microhemorrhages, and presence of cortical superficial siderosis will be evaluated separately using a Bowker's test of symmetry.

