4.7. Interim Analysis

An external Data Monitoring Committee (DMC) is authorized to evaluate results from unblinded interim analyses for the assessment of safety and futility and to recommend any modifications to the study (including stopping the study). Operational details and the decision rules will be provided in the DMC charter.

The DMC will have the responsibility to review accumulating unblinded study data and make recommendations to protect the safety of patients. The DMC will consist of a minimum of 3 members, including a physician with expertise in AD and a statistician. All members will be external to the Sponsor. The approved DMC charter enumerates the roles of the DMC members, the frequency with which it meets, and the structure of their meetings. Study sites will receive information about interim results ONLY if relevant for the safety of their patients.

For safety reviews, the DMC will receive data monitoring results that will include at least the following:

- Demographic characteristics of enrolled subjects
- Adherence to assigned treatment regimen
- Serious adverse events (SAEs)
- Non-serious adverse events
- Adverse events necessitating unblinding at the site or by the sponsor
- Vital signs data
- Central lab data
- Safety MRI data
 - Number of patients with significant treatment-emergent MRI findings, especially Amyloid Related Imaging Abnormalities (ARIA) events such as vasogenic edema or microhemorrhage
 - o Listing of all significant treatment-emergent MRI findings
 - o For patients with ARIA events, standard listings of medical history, concomitant medications, adverse events, baseline demographics
- C-SSRS data

At least 1 interim safety analysis may be conducted for the entire AACQ Study. Operational details and a quantitative framework to provide information for these decisions will be documented in interim analysis Statistical Analysis Plan.

5. Sample Size Determination

Approximately 800 participants will be randomly assigned to 1 of 4 treatment arms in a 1:1:1:1 ratio. It is hypothesized here that in each treatment arm, 10% of participants will not reach primary outcome lock. Below we showed that 720 participants who completed visit 12 can provide more than 80% power to demonstrate that there is over 80% probability that at least one of the alternative dosing regimens will reduce relative risk of ARIA-E by at least 20% compared to the standard dosing regimen.

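### SAP 4.5.1 judges ARIA-E prediction models by BIC without requiring the same participants in each, although some MRI markers come from optional sequences

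*SAP*

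**What the plan says.** SAP 4.5.1 pools the arms ("Information about four dosing regimens will be combined before performing any analysis here") and sets out four types of baseline model for ARIA-E incidence at Week 24:

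- **Model 1:** standard risk factors only.
- **Model 2:** the exploratory MRI markers, 16 by my count of the SAP's list.
- **Model 3:** one marker at a time on top of model 1. "Exploratory MRI endpoints listed above will be added individually to the baseline ARIA-E risk model described in 1".
- **Model 4:** everything together. "The model will include all baseline risk factors described in 1) and all exploratory endpoints described in 2".

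On the criterion: "AIC (Akaike information criteria) as well as BIC (Bayesian information criteria) statistics will be generated for each proposed model above". Then: "While both the AIC and BIC will be generated, the BIC will be used to evaluate the model". An AUC is also computed for each model.

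In the sequence table of Protocol 8.2.7.1, DTI, SWI and task-fMRI carry the footnote "Perform when or where available". The standard sequences, 3D FLAIR and 3D T2 do not.

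SAP 4.5.1 names no common analysis set and no imputation for these models. SAP Appendix 5 deals with missing data only through the repeated-measures model. Protocol 9.3.8 says imputation may be considered and leaves the detail to the SAP, which gives none here.

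**The concern.** BIC has no absolute scale; it evaluates a model only against another model, and only when both are fitted to the same observations. Its main part, minus twice the log-likelihood, is a sum over participants, so removing participants lowers it whether or not prediction improves.

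Standard logistic regression drops anyone with a missing predictor. Of the 16 markers, nine depend on an optional sequence: two SWI counts, five DTI measures, fMRI activation, and the CAA score, which SAP Table 4.2 derives partly from SWI. By default, then, models 2 and 4 and the model-3 fits with those nine markers would use fewer participants than model 1.

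At stake is the tertiary objective of finding characteristics that predict ARIA. An uninformative sequence acquired at only some sites could be credited with improving on standard risk factors, or be placed ahead of a marker that does predict.

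**Working it through.** The plan gives no BIC value and no missing rate, so there is no figure to reproduce. The check asks how many participants must be missing before the smaller sample outweighs BIC's penalty.

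**Inputs from SAP Section 5**
- "Approximately 800 participants will be randomly assigned to 1 of 4 treatment arms in a 1:1:1:1 ratio": N = 800.
- "in each treatment arm, 10% of participants will not reach primary outcome lock": 0.90 × 800 = 720 at Week 24.
- ARIA-E by Week 24: 18.5% in the standard arm, 11.1% in each alternative arm.
- Pooled rate (derived, not stated in the SAP): (18.5 + 3 × 11.1) / 4 = 12.95%.

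**Formulas**
- BIC = −2 log L + k ln(n), with k parameters and n participants.
- Null deviance per participant: d = −2[p ln p + (1 − p) ln(1 − p)].
- Break-even number missing for q uninformative terms: m ≈ q ln(N) / d. This ignores the small change from ln(N) to ln(N − m), and treats the terms as leaving the fit unchanged.

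**Numbers**
- d at 12.95% = −2[0.1295 × (−2.044) + 0.8705 × (−0.139)] ≈ 0.77. Null deviance is about 617 at N = 800 and 555 at N = 720.
- Penalty per parameter at N = 800: ln(800) = 6.68. For 16 terms: 16 × 6.68 ≈ 107.

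| Uninformative terms added | Break-even at N = 800, 12.95% | Range over rates 11.1–18.5% and N 720–800 |
|---|---|---|
| 1 (one marker) | 6.68 / 0.77 ≈ 9 participants, 1.1% | 0.9–1.3% |
| 5 (the DTI measures) | 33.4 / 0.77 ≈ 43, about 5% | 4.3–6.4% |
| 16 (all markers) | 107 / 0.77 ≈ 139, about 17% | 13.6–20% |

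For scale, the null BIC is 616.7 + 6.7 = 623 at N = 800 and 314 at N = 400. Halving the sample lowers it by 309 with no gain in prediction.

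**Simulation.** A logistic simulation used N = 800 and 400 runs per scenario. The following are assumptions, not figures from the documents: case deletion, data missing at random, seven base covariates, a predictive marker with odds ratio 1.5 or 2.0 per SD, one useless marker, and 14 further useless markers in the all-marker model.

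- *Useless marker against model 1, each on its own available cases:* it had the lower BIC in 83–88% of runs with 2% missing, and in 100% with 5% or more. With both models on the same participants: about 0.5–3.5%.
- *Useless marker against a fully observed predictive marker:*

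| Useless marker missing in | Useless marker wins, OR 1.5 | Useless marker wins, OR 2.0 |
|---|---|---|
| 2% | 45% | 2% |
| 5% | 91% | 31% |
| 10% | 100% | 91% |

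On a common set, across all scenarios run, the useless marker won in 0–9% of runs.

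- *All-marker model, which had the fewest participants:* with 30% missing on the useless marker and 10% on the predictive one, it had the lowest BIC of all in only 3–27% of runs. With 30% and 25% missing, it did so in 96–99.5%. On a common set it beat model 1 in 0–0.2%.

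**The case against.** A reader might infer that the SAP plans to fit the models to different participants, and that the model with the most missing data then wins whatever its merit. The documents support neither.

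- **Different samples are a default, not a plan.** The SAP is silent, and Protocol 9.3.8 leaves room for imputation. The fair charge is that the matter is unspecified.
- **Missingness does not decide alone.** BIC also charges for parameters and rewards real fit. The 3–27% result, and the 31% for a strong marker against a useless one missing in 5%, show that the number of terms, the marker's strength and the amount missing all count.
- **Many comparisons should be nearly sound.** White matter burden, PVS, the four volumes and cortical thickness (seven of 16 markers) need no optional sequence, if the volumetric measures come from the standard 3D T1. Models 2 and 4 need the same MRI data, so their samples should nearly coincide. The wording for model 2 speaks of considering markers for inclusion, which may allow a sparse fMRI measure to be left out.
- **The consequence is limited.** The SAP speaks of evaluating, not selecting, and also reports AUC. The tertiary endpoint is an association, which the model coefficients address whatever the BIC. The primary and secondary analyses are untouched.

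All of this narrows the point but does not remove it. Evaluation by BIC is comparative in any case. AUC does not scale with sample size as BIC does, but AUCs from different participants are not strictly comparable either. The next subsection of SAP 4.5.1 restricts its SWI-with-GRE and 3D-with-2D FLAIR correlations to scans with both, so the SAP takes this care elsewhere but not in the model comparison.

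**Conclusion.** The gap is real. SAP 4.5.1 relies on a criterion that is valid only on common participants, does not require common participants, and applies it to markers that the protocol makes optional. The exposed comparisons are model 1 against models 2 and 4, model 1 against the model-3 fits with SWI, DTI, fMRI or CAA markers, and model-3 markers against one another.

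The break-even figures rest on case deletion and on the null deviance at the SAP's design rates. A fitted model 1 has a somewhat smaller deviance per participant, which raises them a little. The simulation adds the assumption of data missing at random. The observed missing rates will decide the actual distortion. The matter is confined to an exploratory analysis and is a cheap improvement.

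**What to change.** Add to SAP 4.5.1:

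1. Models compared by BIC, AIC or AUC are fitted to the same participants.
2. Models 1, 2 and 4 are fitted on one common complete-case set. If task-fMRI makes that set too small, use two tiers, with and without it.
3. For each model-3 comparison, model 1 is refitted on the participants who have that marker. Model-3 markers are compared with one another only on a common set.
4. N and the number of ARIA-E events are reported for every model.

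Prespecified imputation of missing predictors would be an acceptable alternative.

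The cost is a few sentences and some refits, with no new data. The downside is that some model-1 results are shown on a smaller sample; model 1 on all available participants can still be reported, outside the BIC comparison.

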4.6.8. Safety MRIs

Treatment-emergent white matter disease and other abnormality findings will be summarized as incidence in safety analysis set.

To evaluate white matter changes over time, a shift table from baseline to selected visits via treatment arm will be created from the following categories:

- 0 = No lesions
- 1 = Focal lesions
- 2 = Beginning confluence of lesions

• 3 = Diffuse involvement of entire region

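### SAP 4.5.1 has no model with a standard-sequence white-matter score, so the planned prediction models cannot show whether 3D FLAIR adds anything over the standard read

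*SAP*

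**What the plan says.** SAP 4.5.1 (Prediction of ARIA) lists four types of baseline logistic model for ARIA-E at Week 24.

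- **Model 1** holds known risk factors: APOE e4 genotype, the microhemorrhage count from the standard sequences, and "presence of superficial siderosis at baseline (determined by standard safety sequences), amyloid centiloid at baseline, mean arterial pressure, and anti-hypertensives". White-matter disease is not among them.
- **Model 2** holds the exploratory MRI markers, including "white matter disease burden from 3D FLAIR".
- **Model 3**: "Exploratory MRI endpoints listed above will be added individually to the baseline ARIA-E risk model described in 1".
- **Model 4** combines the terms of Models 1 and 2.

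Two source rules follow. For SWI, "the counts of microhemorrhages and superficial siderosis will come from baseline SWI instead of its standard safety MRI equivalent". For 3D FLAIR, "white matter burden score will come from 3D FLAIR instead of the standard safety sequence MRI equivalent". AIC, BIC and AUC are produced for the models, and BIC is the criterion used to evaluate them.

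A separate part of 4.5.1 compares standard with exploratory sequences. For white-matter burden it plans a baseline contingency table with Bowker's test. SAP 4.6.8 also plans a white-matter summary on a 0 to 3 scale: "To evaluate white matter changes over time, a shift table from baseline to selected visits via treatment arm will be created".

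**The concern.** The two source rules have the same form, but only one has a counterpart in Model 1. The SWI reads have standard microhemorrhage and siderosis reads to stand against. The 3D FLAIR white-matter score has none. Model 3 versus Model 1 therefore compares some white-matter information with no white-matter information.

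Two different things could produce a better BIC or AUC: knowing the white-matter burden at all, or reading it on the 3D sequence. The exploratory endpoint in SAP 1.1 is worded as an association of exploratory MRI sequences with ARIA, so the distinction matters for how a gain is described. At stake is the interpretation of one exploratory marker.

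**Working it through.** There is no plan figure to reproduce, because the point concerns which terms are in which model.

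**Step 1: where white-matter burden appears.**

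| Model | Standard-sequence score | 3D FLAIR score |
|---|---|---|
| 1 | no | no |
| 2 | no | yes |
| 3 (white-matter version) | no | yes |
| 4 | no | yes |

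No pair of planned models differs only in the sequence on which white matter was read.

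**Step 2: does another analysis fill the gap?** Bowker's test asks whether disagreements between the two reads are symmetric. It does not use ARIA-E. The remaining 2D versus 3D FLAIR comparisons concern ARIA-E severity, time to first event and resolution, not baseline white matter.

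**Step 3: how BIC behaves.** BIC = −2 log L + k ln(n). For one added term, the gain over Model 1 is the likelihood-ratio statistic minus ln(n). With n = 720 (SAP 5), ln(720) = 6.58. If white matter is unrelated to ARIA-E, the statistic averages about 1, so the expected gain is about 1 − 6.58 = −5.6. Between Model 1 + 3D score and Model 1 + standard score the penalties cancel if both scores are coded alike, leaving only the difference in fit.

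**Step 4: illustration.** Inputs from SAP 5 are 720 participants, an ARIA-E rate of 18.5% in the standard arm and 11.1% in each alternative arm. The pooled rate is (18.5 + 3 × 11.1)/4 = 12.95%, or 720 × 0.1295 = 93 events. Assumed, because the documents give nothing: the white-matter odds ratio per SD, the covariate distributions and effects, a continuous score, and two reads that each correlate 0.9 with true burden. There were 300 simulated trials per row, and AUC is in-sample.

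| OR per SD | Mean BIC gain, 3D over Model 1 | BIC prefers 3D to Model 1 | AUC gain over Model 1 | Mean BIC gain, 3D over Model 1 + standard | BIC prefers 3D to Model 1 + standard |
|---|---|---|---|---|---|
| 1.0 | −5.6 | 1% | 0.002 | 0.0 | 48% |
| 1.25 | −2.4 | 19% | 0.010 | +0.1 | 52% |
| 1.5 | +4.4 | 71% | 0.026 | −0.2 | 47% |
| 1.75 | +13.8 | 96% | 0.045 | −0.1 | 51% |
| 2.0 | +23.6 | 100% | 0.064 | +0.9 | 57% |

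The first row matches Step 3. The mean AUC gain over Model 1 + standard is 0.000 or 0.001 throughout. The last column should be 50% in every row because the reads are exchangeable by construction, so departures are simulation noise. With 800 participants the preference over Model 1 is 25% at an odds ratio of 1.25 and 79% at 1.5.

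A second set of simulations, with four-category reads and event rates of 13% to 18.5%, gave 62% to 82% at an odds ratio of 1.5. Against the standard score it gave 46% to 53% over all settings.

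**The case against.** The strongest reply is that Model 3 answers the question the objective asks, namely which characteristics predict ARIA. Most other exploratory markers (perivascular spaces, diffusion, functional and volumetric measures) also lack a counterpart in Model 1, so adding a new marker to known risk factors is the normal Model 3 contrast. The 3D FLAIR sentence may simply name which of two reads feeds the models. All of this stands, and on that reading the SAP does not contradict itself. White matter still differs from those markers in one respect: the SAP itself recognises a standard equivalent and then uses it in no prediction model.

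It would also be too much to say that the SWI comparison is already like for like. Taken literally, adding SWI endpoints to Model 1 keeps the standard counts beside them, so whether a swap is meant is unclear.

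A reader might infer that the sponsor will credit any gain to the 3D sequence, or that the trial could wrongly support adding it to practice. The documents do not support either inference. The SAP nowhere says a better BIC or AUC will be read that way, and protocol 8.2.7.1 confines the exploratory sequences to exploratory analysis, outside participant management. Close agreement in the baseline table would also warn against such a claim, although it would not test it.

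Finally, the zero gain over the standard score is built into the simulation by assuming equally accurate reads. It shows the mechanism and is not evidence that 3D FLAIR is no better. Protocol 5.2 excludes severe white matter disease, which narrows the range and may shrink any gain.

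**Conclusion.** The point holds in a limited form. No planned model separates the predictive value of white-matter burden from that of the 3D FLAIR sequence, and the agreement analysis does not do so either. A gain of Model 3 over Model 1 would be a valid finding about white-matter burden as read on 3D FLAIR, but it would say nothing about 3D FLAIR relative to the standard read.

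How much could be misattributed depends on a white-matter effect that the documents do not give. With equally accurate reads assumed, BIC shows no gain on average at an odds ratio per SD of about 1.25 or below, although individual trials may. A gain is likely at 1.5 or above. The analysis is tertiary and concerns one of about sixteen candidate markers, so the priority is low.

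**What to change.** Keep Model 1 unchanged. Add one reference model: Model 1 plus the baseline white-matter score from the standard safety sequences. Compare BIC and AUC for Model 1 + 3D FLAIR white-matter score with that reference, on the same participants and with both scores coded alike. State that a gain over Model 1 alone will be described as a gain from white-matter burden, and that only a gain over the reference bears on the sequence. It would help to say in the same edit whether the SWI counts replace the standard counts in Models 3 and 4 or are added to them.

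The cost is one more logistic fit and a sentence or two in SAP 4.5.1. No new data should be needed, because the agreement table in 4.5.1 already requires a standard baseline score and 4.6.8 plans a white-matter shift table from baseline. The SAP does not name the standard sequence used for that score, so it should be named.

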The Bayesian power calculation was performed through simulations in both data generation and model fitting steps. In the data simulation stage, 1000 ARIA-E data sets were generated for every treatment arm. It was assumed that ARIA-E rate by Week 24 in the standard dosing regimen was 18.5% based on observations from AACI Addendum 9 data. In each alternative dosing regimen, ARIA-E rate was set to be equal to 11.1%, which translates to 40% relative risk reduction in ARIA-E compared to standard dosing regimen.

In the model fitting stage, a normal prior, N(0,4) was assigned to individual slope parameter of Arm 2, 3, and 4, respectively in the Bayesian logistic regression model. The intercept parameter was given a normal mixture prior, $0.5 \times N(-1.48, 4) + 0.5 \times N(-1.48, 30.19)$. The component prior mean (-1.48) in the mixture prior is equal to the natural log odds ratio of ARIA-E rate at 18.5% observed from historical study. For any simulated ARIA-E data with a complete sample size of 720, posterior samplers of RD_{21} , RD_{31} , and RD_{41} were simulated from 3 Markov chains with each chain composed of 10000 iterations after 10000 burn-ins. Among 1000 datasets generated, 927 satisfied at least one of the following probability statements:

```
Pr(RD_{21} \ge 0.2 \mid \text{simulated 24-week ARIA-E data}) > 0.8;

Pr(RD_{31} \ge 0.2 \mid \text{simulated 24-week ARIA-E data}) > 0.8;

Pr(RD_{41} \ge 0.2 \mid \text{simulated 24-week ARIA-E data}) > 0.8.
```

Hence, the reported power was 92.7% based on simulations.

In the null scenario where all the dosing regimens have the same true ARIA-E rate of 18.5% by Week 24, the false positive rate was controlled at 5% one-sided, or equivalently 10% two-sided.

The power and false-positive rate of the study were determined by simulations using R 4.1.2. Particularly, posterior samplers were generated through rjags package in R.

6. Supporting Documentation

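### The ARIA-E prediction models, with up to about 23 slopes, are reported with an uncorrected in-sample AUC, which overstates discrimination most for the largest models

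*SAP*

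**What the plan says.** SAP 4.5.1 pools the arms: "Information about four dosing regimens will be combined before performing any analysis here". It then describes four types of logistic model for Week 24 ARIA-E.

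- Model 1 uses six known baseline risk factors.
- Model 2 uses the exploratory MRI markers.
- Model 3 adds the MRI markers to model 1 one at a time.
- Model 4 is the union: "The model will include all baseline risk factors described in 1) and all exploratory endpoints described in 2".

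AIC and BIC are produced for every model, and BIC is named as the one used for evaluation. The same paragraph gives the AUC a separate job: "AUC (area under the curve) will be computed to tell how each model is capable of distinguishing between ARIA-E subjects and ARIA-E free subjects". It adds that a larger AUC means better discrimination. The SAP version history shows that the ROC curve and AUC were added in version 3.0 to measure classification.

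Neither document mentions a hold-out sample, cross-validation, bootstrap correction or external data set for these models. SAP 4.5.1 does not say how missing predictors are handled, or whether the models share one set of subjects.

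**The concern.** An AUC computed in the data that produced the coefficients is too high, because the fit has partly adapted to chance patterns. The excess grows with the number of slopes and shrinks with the number of events. Model 4 has the most slopes for the same events, so its AUC is inflated more than that of model 1.

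One objective in Protocol Section 3 is to explore what predicts ARIA. A reader of the report will naturally compare the AUC with and without the MRI markers. That comparison can show a gain when the markers carry no information, and the reported level of discrimination would not be reached in new patients.

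**Working it through.** **Inputs from the documents**

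- Subjects: SAP Section 5 assumes that "10% of participants will not reach primary outcome lock", so 800 × 0.9 = 720, or 180 per arm. It states that "720 participants who completed visit 12 can provide more than 80% power".
- Rates in percent: "ARIA-E rate by Week 24 in the standard dosing regimen was 18.5", and in each alternative arm the "ARIA-E rate was set to be equal to 11.1". Check: 18.5% × 0.6 = 11.1%.
- Model 1 slopes: APOE 2 (three levels, SAP 4.3.2), microhemorrhage count 1, siderosis 1, centiloid 1, mean arterial pressure 1, antihypertensives 1. Total 7.
- Model 2 slopes: 16 markers named, taken as one slope each.
- Model 4 slopes: 7 + 16 = 23, or 21 if the two SWI counts replace the two standard counts.

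**The plan's own figure.** The SAP gives no figure for these models. Its power of 92.7%, which uses the same n and rates, was recomputed with 180 per arm. The result was 92.9% or 91.7% under two readings of the intercept prior's second argument. It was 84.9% with every second argument read as a variance, and 73.6% with every one read as a precision. That ambiguity is a separate matter; the n and event rates are those the SAP used.

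**Events per slope**

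- Planning rates: 180 × (0.185 + 3 × 0.111) = 93.2 events. Per slope: 93.2/7 = 13.3 (model 1), 93.2/16 = 5.8 (model 2), 93.2/23 = 4.1 (model 4).
- All arms at 18.5%: 720 × 0.185 = 133.2 events, or 133.2/23 = 5.8 per slope in model 4.

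**Simulation.** Each data set had 7 risk-factor slopes and 16 independent normal MRI markers unrelated to ARIA-E. Models were fitted by maximum likelihood. The AUC was taken in the fitting data and in 20,000 new subjects, with 300 to 600 data sets per setting. The risk-factor effects are assumed moderate, and n=360 and n=180 are assumed complete-case sizes. Differences are from unrounded means.

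| Setting | Model 1, fitting / new | Model 4, fitting / new | Model 4 − model 1, fitting / new |
|---|---|---|---|
| n=720, 93 events | 0.678 / 0.647 | 0.716 / 0.619 | +0.038 / −0.028 |
| n=720, 133 events | 0.673 / 0.654 | 0.704 / 0.630 | +0.031 / −0.025 |
| n=720, 93 events, no predictor informative | 0.578 / 0.500 | 0.647 / 0.500 | +0.069 / 0.000 |
| n=360, 47 events | 0.694 / 0.636 | 0.761 / 0.599 | +0.068 / −0.038 |
| n=180, 23 events | 0.718 / 0.606 | 0.826 / 0.565 | +0.108 / −0.041 |

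Model 4 had the higher fitting-data AUC in every data set. A repeat simulation at n=720 gave 0.682 / 0.652 for model 1 and 0.719 / 0.624 for model 4. The best single noise marker added to model 1 (model 3) raised its fitting-data AUC by 0.010 to 0.039. MRI-only model 2 gave 0.624 / 0.500 at n=720 with 93 events, below model 1.

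**BIC on the same subjects.** The penalty for 16 extra slopes is 16 × ln(720) = 105. Noise is expected to reduce the deviance by about 16, so model 4 should be worse by 105 − 16 = 89. The simulated mean was 88.7, and BIC preferred model 4 in 0 of 600 data sets. AIC preferred it in 0% to 4% across settings.

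**BIC on different subjects.** The footnote to the MRI sequence table (Protocol 8.2.7.1) makes DTI, SWI and task fMRI subject to availability. If each model used its own complete cases (an assumption, since the SAP is silent), the smaller model 4 sample would lower its BIC mechanically. At an event rate of 93.2/720 = 12.95%, each subject contributes about −2 × [0.1295 ln 0.1295 + 0.8705 ln 0.8705] = 0.77 to the deviance. The 89-point margin is therefore gone after about 89/0.77 ≈ 115 missing subjects (n ≈ 605). In simulation with model 1 on 720 subjects, BIC wrongly preferred model 4 in 31–42% of data sets at n=612, 94–98% at n=576 and 100% at n=504.

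**The case against.** The strongest reply is that the SAP does not choose models by AUC. A reader might infer that it does, and that the question of whether MRI adds to known risk factors is therefore biased towards yes. The text does not support that. BIC is the named criterion, it penalises size, and on a common set of subjects it was never misled by noise markers. That part of the reply stands.

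A reader might also infer that in-sample AUC always favours the bigger model. It does not. Model 2 is not nested with model 1, and with truly predictive risk factors its AUC was lower at n=720 (0.624 against 0.678). It was higher only with no signal at all (0.623 against 0.578) or at n=180 (0.746 against 0.718). Any SWI substitution also means that model 4 does not strictly contain model 1.

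The no-signal row should not be taken as the expected size. Protocol 2.2 says APOE ε4 carriers have greater ARIA-E risk, and assumed moderate effects roughly halve the false gain, from 0.069 to 0.038.

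Finally, the analysis is tertiary. No decision rule, AUC threshold or participant management depends on it. This limits the weight of the point but does not remove it. BIC ranks models and does not correct the AUC, which the SAP reports as its measure of discrimination. The protection from BIC also needs a common set of subjects, which the plan does not require.

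**Conclusion.** The point holds in a limited form. The AUC is a second measure beside BIC, it is not corrected for optimism, and it will be too high. At n=720 with about 93 events the excess is about 0.03 for model 1 and 0.10 for model 4, so noise MRI markers appear to add about 0.04 while discrimination in new subjects falls by about 0.03. With 133 events the excess in model 4 is about 0.07. With an assumed 360 complete cases it is about 0.16.

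The false gain applies to models that add markers to model 1 (models 3 and 4), and not generally to model 2.

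These sizes rest on assumptions outside the documents: risk-factor effects, APOE and microhemorrhage frequencies, independent normal markers with one slope each, 23 slopes in model 4, and the complete-case sizes. The direction for models 3 and 4 was the same in every setting run. The primary and secondary results are unaffected. Label: cheap improvement.

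**What to change.** Amend SAP 4.5.1 as follows.

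1. Keep BIC as the stated criterion.
2. Fit and compare models 1 to 4 on one common set of subjects, define that set, and report its size and number of events.
3. For each model, report a bootstrap optimism-corrected AUC (for example 500 resamples), repeating the whole fitting procedure in each resample. This includes any choice of marker under model 3.
4. Report the corrected AUC difference from model 1 with its interval. If the uncorrected AUC is shown, label it as such.

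A penalised fit for models 2 and 4 is optional.

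The cost is a few SAP sentences and some computing time, with no new data. The reported AUCs will be less favourable. The common set will exclude subjects without the optional sequences, so model 1 can also be shown on all available subjects as a separate result.
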